10.4.4 Exploratory hypotheses examining different client subtypes within STAGE-12

10.4.4.1 Objective

To examine the relative differences in 12-step meeting attendance and involvement and substance use outcomes of different client subtypes (e.g., ethnic/racial groups, gender, drug of choice, psychiatric severity, readiness to change).

10.4.4.1.1 Hypothesis

Individuals identified as ethnic minorities will be less likely to attend 12-step meetings and engage in 12-step activities than are Caucasian individuals.

10.4.4.1.2 Hypothesis

Men are more likely to attend 12-step meetings and engage in 12-step activities than are women.

10.4.4.1.3 Hypothesis

Individuals with higher levels of psychiatric severity, as assessed by the Addiction Severity Index, are less likely to attend 12-step meetings and engage in 12-step activities than are those with lower levels of psychiatric severity.

10.4.4.1.4 Hypothesis

Participants with different types of drug dependency (cocaine vs. methamphetamine) will differ with respect to their 12-step meeting attendance and engagement in 12-step activities.

10.4.4.1.5 Hypothesis

Individuals with higher levels of readiness to change their substance use behaviors are more likely to attend 12-step meetings and engage in 12-step activities than are those with lower levels of readiness to change.

The outcome variable will be 12-step meetings meeting attendance (yes/no). For each of the hypotheses listed above the data will be analyzed using the proportional mean model for recurrent events similar to the model for mean number of positive drug screens in 10.4.1.1.2. In this model, variable Z_i will be an indicator of a particular group of interest (e.g., ethnic minorities vs. Caucasian in the analysis for 1.3.4.1)

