3.4 Low Rates of 12-Step Attendance and Involvement Following Treatment As Usual

Despite the potential benefits associated with 12-step involvement and attendance, from 60-70% of substance abusers have never attended a 12-step meeting. Harris, et al. (Harris, Best et al. 2003) found that while about 75% of alcoholics entering residential treatment reported that they had attended AA meetings previously, only 16% indicated that they had ever worked on any of the 12 Steps. Of the 150 patients who were interviewed, only 38% reported a positive attitude toward AA. Although drug abusers appear to hold a somewhat more positive attitude toward 12-step groups than do alcoholics (Best, Harris et al. 2001), Rawson, et al. (Rawson, Obert et al. 1991) found that long-term regular involvement in 12-step groups and activities was initiated by fewer than 30% of cocaine abusers receiving outpatient treatment. The rate of 12-step attendance was only somewhat higher, 40%, among those discharged from a 28-day inpatient cocaine treatment program. This low rate occurred despite what was described as "strong encouragement" to attend from each of the treatment programs involved and the availability of 12-step meetings on site (Rawson, Obert et al. 1991). Similarly, Weiss, et al. (Weiss, Griffin et al. 1996) found that only 34% of clients enrolling in the NIDA Collaborative Cocaine Treatment Study (CCTS) had attended a 12step meeting in the week prior to their beginning treatment. This pretreatment participation was prognostic of early success in achieving abstinence in this outpatient trial. Of self-help attenders who actively participated, 55% initiated abstinence within the next month, compared with 40% of non-attenders and 38% of non-participating attenders. Over the follow-up period, only a third of the clients (33.6%) were classified as consistently high meeting attenders, while 47.9% were classified as consistently low attenders, and 18.5% had a decreasing attendance pattern across time. A similar pattern was found for involvement in 12-step activities: 35.4% of subjects were classified in the high participation group, with 47.5% in the low and 17.0% in the decreasing participation groups. Low and inconsistent involvement was associated with poorer outcomes (Weiss, Griffin et al. 1996; Weiss, Griffin et al. 2000; Weiss, Griffin et al. 2005). The five clinical sites participating in the CCTS evidenced a high degree of variability in meeting attendance by the sixth month of the trial, ranging from 20% to 69% of clients attending meetings. This occurred despite all sites having used the manual-guided Group Drug Counseling (Daley, Mercer et al. 1999), which recommended and emphasized self-help meeting attendance, as their standard "treatment as usual" (TAU). Variability in the recommended or required frequency of attendance was also noted in the TAU of

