5.2 Number of Sites and Participants

A target of approximately 400 participants from approximately 10 CTPs will be recruited. The goal is to have a sufficient number of interested and qualified CTPs available so that replacement of a CTP can be made in the event of program closure or withdrawal. Each CTP will have approximately 40-50 participants with 20-25 participants in each condition. The overall sample size and number of subjects per participating CTP may be adjusted based on the outcome of a blinded variance check to be conducted after approximately 200 subjects have been randomized (see Section 10.7). An attempt will be made to recruit approximately 50% female participants. In addition, efforts will be made to recruit a sample of study participants that reflects the proportion of minorities in the community where the site is located. Potential participants must satisfy study inclusion and exclusion criteria, listed in section 5.3.3.1

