10.2 Randomization

Participants will be randomized to one of the two treatment conditions. Randomization will be stratified by site and by whether the participant was court-mandated for treatment vs. not court-mandated. The randomization process will be conducted in a centralized process through the Data and Statistical Center (DSC).

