10.4.1.1.2 Hypothesis

STAGE-12 will result in fewer positive drug screens/urinalyses than TAU.

The outcome variable will be positive drug screen (yes/no) measured at baseline, weeks 4, 8/end of treatment, 3 months and 6 months. The data will be analyzed using the proportional mean model for recurrent events (Lin et al., 2000):

$$\mu_Z(t) = E\{N_i(t) | Z_i\} = \exp(\lambda_D Z_i)\mu_0(t),$$

where Z_i = 0 if the participant belongs to TAU group and Z_i = 1 if the participant belongs to STAGE-12 group; $N_i(t)$ is the total number of positive drug screen results for participant i at the time of assessment t; λ_D is the effect of the STAGE-12 treatment. The advantage of the proportional mean model is that it does not assume the nature of the influence of prior events on the future recurrence. The following statistical hypotheses will be assessed: H_0 : λ_D =0 vs. H_1 : $\lambda_D \neq 0$. Rejection of the null hypothesis with λ_D < 0 would indicate that STAGE-12 treatment results in fewer positive drug screens than TAU. The analysis will be performed using PROC PHREG with TIE=DISCRETE option for handling ties event times and COV(AGGREGATE) option to request the robust sandwich covariate matrix estimate.

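### The exploratory client-subtype models in 10.4.4 carry no site term, so a site difference in 12-step attendance can be reported as a subtype difference; the documents support this best for ethnicity

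*Protocol*

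**What the plan says.** Section 10.4.4 lists five hypotheses on who attends 12-step meetings: ethnic minority versus Caucasian, men versus women, psychiatric severity, cocaine versus methamphetamine, and readiness to change. The paragraph closing 10.4.4.1.5 gives one analysis for all five: a proportional mean model on attendance (yes/no), "similar to the model for mean number of positive drug screens in 10.4.1.1.2". It then adds only that "In this model, variable Z_i will be an indicator of a particular group of interest".

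The template is in 10.4.1.1.2: "The data will be analyzed using the proportional mean model for recurrent events", with mean function exp(λ_D Z_i) μ_0(t), fitted in PROC PHREG with a robust sandwich variance. There the covariate is the arm: "where Z_i = 0 if the participant belongs to TAU group and Z_i = 1 if the participant belongs to STAGE-12 group". No site, court-mandate or other term appears in it, and nothing in 10.4.4 adds one.

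Three other places bear on the point:
- Section 10.2: "Randomization will be stratified by site and by whether the participant was court-mandated for treatment vs. not court-mandated". This balances the arms within site. It does nothing for subtypes.
- Section 3.4, on an earlier five-site cocaine trial: "variability in meeting attendance by the sixth month of the trial, ranging from 20% to 69% of clients attending meetings". Sections 3.4 and 3.6 add that programmes in a methamphetamine trial ranged from recommending attendance to requiring it at very different intensities.
- Section 5.2: efforts will be made to recruit a sample that "reflects the proportion of minorities in the community where the site is located".

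The primary model in 10.3.1 has site-specific intercepts, site-specific slopes and a court-mandate covariate.

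**The concern.** A one-covariate model with a common baseline is acceptable in 10.4.1.1.2 because randomisation within site makes arm and site independent by design. That protection is lost when the arm is replaced by ethnicity or drug type. The coefficient then mixes two things: any difference between client types attending the same clinic, and the difference between clinics that happen to serve different client types. A clinic that requires meetings and serves mostly one group will make that group look like better attenders. The robust variance does not help: it corrects the standard error for repeated observations on a participant and leaves the point estimate where it is.

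At stake is how directional statements about ethnic minorities, women or people with psychiatric illness are read. A clinic's attendance policy could be written up as a property of the clients.

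**Working it through.** The protocol gives no figure for these tests, so there is nothing to reproduce. The check has two parts.

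**1. What the crude contrast converges to.** Take 10 equal sites (10 is the approximate number in section 5.2) with attendance evenly spaced from 20% to 69% (section 3.4), no subtype effect within any site, and subtype share falling evenly from 70% to 30% as attendance rises. The shares are an assumption.
- Mean attendance = (0.20 + 0.69)/2 = 0.445; mean share = 0.50.
- Variance of the site position i/9, i = 0..9: [(100 − 1)/12]/81 = 0.1019.
- Covariance of share and attendance = −0.40 × 0.49 × 0.1019 = −0.0200.
- Attendance in the subtype = 0.445 − 0.0200/0.50 = 0.405; in the others 0.445 + 0.0200/0.50 = 0.485.
- Crude ratio = 0.405/0.485 = 0.84, although the within-site ratio is 1.

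This is a deliberately unfavourable alignment, used to show the mechanism. If share were unrelated to site, or attendance the same everywhere, the covariance would be zero and the ratio 1.

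**2. Rejection rates when site mix and site attendance are paired at random.** Inputs:
- From the protocol: about 10 sites, about 400 participants, attendance range 20% to 69%, four post-baseline assessments. The two-sided 0.05 level is stated for the primary outcome and assumed here.
- Assumed: the subtype shares, within-person correlation 0.4, complete follow-up, evenly spread site rates.
- Test as written: log ratio of mean event counts with participant-level robust variance, a stand-in for the single-covariate proportional mean test at common visit times. Comparator: the same with a separate baseline per site.

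False-positive rate against a within-site null:

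| Subtype share across sites | 400 participants, no site term | 200 participants (STAGE-12 only), no site term |
|---|---|---|
| 10% to 90% | 24% | 15% |
| 20% to 80% | 17% | 11% |
| 35% to 65% | 8% | 6% |

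With site strata the rate is about 5% to 6%.

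Sensitivity:
- Site attendance spanning only 35% to 55%: about 8% with 400 participants at share 10% to 90%, and 5% to 7% with 200 at every share tried.
- Lower within-person correlation (beta-binomial with parameter sum 6, so 1/(6 + 1) = 0.14), 400 participants, attendance 20% to 69%, random pairing: 32% (share 10% to 90%), 12% (30% to 70%), 5% (40% to 60%).
- Same setting, but share running against attendance: 100% (10% to 90%), 70% (30% to 70%), 19% (40% to 60%). Site strata bring these to about 4% to 5%.
- No site difference in attendance: about 5% even at share 10% to 90%.

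The excess appears only when both ingredients are present. Court mandate was not simulated.

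**The case against.** **The crude difference may be the target.** Section 10.4.4.1 asks for relative differences between subtypes, and the hypotheses ask which group is more or less likely to attend. A pooled comparison answers that descriptively, and calling its rejections false presupposes a within-site null. This stands in part: the rates above hold only relative to that null. But the objective is framed around types of client, and the protocol does not say the result is to be read as a mix of client and clinic. Reporting both contrasts settles it.

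**Adjustment for exploratory models belongs in the SAP.** The word similar leaves some room. Yet the protocol wrote out the equation, procedure and options and then redefined only Z_i. That is a model stated without site, not a detail left open.

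**The inputs are soft.** This stands. The 20% to 69% range is the observed extremes of five sites at one time in another trial, sampling error included. No site mix is given for any subtype. Section 5.2 describes an effort to mirror local communities and gives no proportions; for gender it aims at about 50% women overall. The 10.4.1.1.2 model also specifies discrete tie handling, which at common visit times gives an odds-type fit, so the simulated test approximates the specified one. The confounding does not depend on that scale.

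**The heading limits the analysis to STAGE-12.** On that reading arm is constant, its absence is no defect, and the 200-participant column applies.

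**Conclusion.** The point holds as a risk confined to exploratory analyses: a site difference in attendance can be reported as a subtype difference. It is best supported for ethnicity, where the protocol itself ties the mix to each site's community and reports large site differences in attendance. For drug type, severity, readiness and gender it is conditional on clustering that the documents do not show. The size under the stated assumptions is about 8% to 25% false positives with 400 participants and 6% to 15% with about 200, against about 5% to 6% with site strata, and little above nominal under milder inputs.

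Four stronger readings are tempting and are not supported:
- That the model will declare subtypes different. It can; both conditions are needed, and their alignment decides the size.
- That all five subtypes are affected. Assuming drug type split 5%/95% between halves of the sites gives 45% rejections, but no passage supports that split.
- That spurious ratios of 0.76 to 1.34 (the middle 95% at share 10% to 90%) measure the bias. Much of that width is ordinary sampling error: at share 40% to 60%, with rejection near nominal at 6%, the range is already 0.84 to 1.19.
- That the urine comparison in 10.4.1.1.2 is biased. Arm is randomised within site. With an assumed site positivity of 20% to 69%, the model as written rejects about 3% to 4% of the time under the null, which is slightly conservative.

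The primary analysis is unaffected, and section 10.4 already treats significant secondary findings as exploratory.

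**What to change.** In the analysis paragraph of 10.4.4.1.5, give the proportional mean model a separate baseline mean function per site and include court mandate as a covariate, so that each coefficient is a within-site contrast consistent with 10.3.1. Add arm only if both arms are pooled, and state which population is meant, given the within-STAGE-12 heading. Report the crude contrast alongside, labelled descriptive. Where a subtype is nearly site-specific, say that little within-site information exists and report that subtype descriptively only.

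This takes one strata statement and a covariate, using data already collected. The price is a wider interval for subtypes concentrated in few sites, and slight small-sample inflation there (about 7% in the 5%/95% drug-type case).

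Optionally, stratify the urine model by the randomisation strata for a few points of power. The gain is not cleanly measured: 76% against 81% power came with type I error of 3.6% against 6.1%, so the two are not like for like.

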severity that allow the measurement of change across treatment or time. The Psychiatric Severity Composite will be used as a predictor variable. In addition to evaluating the impact of the intervention on substance use and 12-step engagement, the ASI-Lite will be used to assess the impact on more general psychosocial function through the Medical, Employment, Legal, Family/Social, and Psychiatric Status indices of the measure.

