5.4.3.4.3 Stages of Change Readiness and Treatment Eagerness Scale (SOCRATES)

The SOCRATES (Miller and Tonigan 1996) is a 20-item self-report measure of clients' readiness to change their substance use behaviors. It will be administered at the baseline and End of Treatment/week 8 visits. Originally, the 40-item scale had five subscales based on Prochaska and DiClemente's Stages of Change model of addictive behaviors. The SOCRATES was developed and its psychometric properties determined in Project MATCH. Isenhardt (Isenhart 1994) has used a modified version of the SOCRATES that includes references to drug use with a broader range of substance abusers; this is the version that will be employed. The current version has three subscales: Taking steps, Recognition of a problem, and Ambivalence. The instrument is intended to assess which of these stages the individual is in at the time of the assessment. Psychometric properties of the SOCRATES are good to excellent. Cronbach's alpha for the three scales ranged from .88 to .96, while test-retest reliability ranged from .83 to .99. The final three-factor solution seems stable. Inclusion of a measure of readiness to change is important in light of the findings by Laudet (Laudet 2003). Major obstacles to participation in 12-step programs centered on motivation and readiness for change and on perceived need for help, rather than on aspects of the 12-step program often cited as points of resistance (e.g., religious aspect and emphasis on powerlessness).

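### The exploratory subtype analyses (Protocol 10.4.4) code two graded baseline scores, psychiatric severity and readiness to change, as group indicators, which costs power for no gain

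*Protocol*

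**What the plan says.** The analysis paragraph at the end of Protocol 10.4.4.1.5 covers all five subtype hypotheses: "For each of the hypotheses listed above the data will be analyzed using the proportional mean model for recurrent events". The model is to resemble the drug-screen model of 10.4.1.1.2, and "variable Z_i will be an indicator of a particular group of interest". In that template the covariate is binary: "where Z_i = 0 if the participant belongs to TAU group and Z_i = 1 if the participant belongs to STAGE-12 group". The one worked example of the subtype covariate is minority versus Caucasian.

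Two of the five hypotheses concern levels of a score:

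- 10.4.4.1.3: "Individuals with higher levels of psychiatric severity, as assessed by the Addiction Severity Index, are less likely to attend 12-step meetings".
- 10.4.4.1.5: "Individuals with higher levels of readiness to change their substance use behaviors are more likely to attend 12-step meetings".

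Section 5.4.3.1.3 says of the first score that "The Psychiatric Severity Composite will be used as a predictor variable". Section 5.4.3.4.3 describes SOCRATES as a 20-item measure: "The current version has three subscales: Taking steps, Recognition of a problem, and Ambivalence". No subscale is chosen for the readiness hypothesis.

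The response is given as yes/no: "The outcome variable will be 12-step meetings meeting attendance (yes/no"). Section 5.4.2.1 collects attendance in days on the Substance Use Calendar, and 10.4.2.1.1 analyses the same construct as percent of days.

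**The concern.** An indicator is the right coding for a category. For a graded score it treats everyone on one side of the cut as alike and everyone on the other side as alike, so differences within each side no longer contribute. The result then also depends on where the cut falls. The proportional mean model does not require this. Its mean function, exp(λZ)μ0(t), takes a continuous Z unchanged, and exp(λ) becomes the ratio of mean counts per unit of the score.

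What is at stake is limited: how far a null or weak result on severity or readiness can be interpreted, within analyses that 10.4.4 itself labels exploratory.

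The yes/no response raises a second, related question. If attendance is scored once per assessment, as the drug screen is, the day counts on the calendar are not used in these analyses.

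**Working it through.** **The plan's own figure.** There is none to reproduce. The protocol gives no power, sample size, cut-point or score distribution for the subtype tests.

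**Inputs**

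- Covariate coding: group indicator for all five hypotheses (10.4.4.1.5), 0/1 in the template (10.4.1.1.2).
- Sample size: about 200 per arm, so about 400 (10.6). At the assumed 70% retention, 0.70 × 400 = 280.
- Test level: two-sided 0.05. This is stated for the primary test in 10.6 and assumed here.
- Assumptions not in the protocol: a roughly normal score, a linear effect, and a cut at the median or at the top quarter.

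**Information kept after a cut.** For a normal score with share q above the cut c, relative efficiency (RE) against the uncut score is

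RE = φ(c)² / [q(1 − q)].

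- Median: c = 0, φ = 0.3989, so RE = 0.1592 / 0.25 = 0.637. About 36% is lost.
- Top quarter: c = 0.6745, φ = 0.3178, so RE = 0.1010 / 0.1875 = 0.539. About 46% is lost.

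In participants, 400 × 0.637 ≈ 255 and 400 × 0.539 ≈ 215.

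**Power.** If the uncut score has a given power, with normal quantile z_power, the indicator has power Φ[(1.96 + z_power)√RE − 1.96].

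| Power, uncut score | Median cut | Top-quarter cut |
|---|---|---|
| 80% (z = 0.842) | Φ(2.802 × 0.798 − 1.96) = Φ(0.275) = 61% | Φ(2.802 × 0.734 − 1.96) = Φ(0.096) = 54% |
| 90% (z = 1.282) | Φ(3.242 × 0.798 − 1.96) = Φ(0.626) = 73% | Φ(3.242 × 0.734 − 1.96) = Φ(0.419) = 66% |

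The 80% and 90% starting points are illustrations only. A Fisher-z calculation with an assumed correlation of 0.14 gives the same picture. With 400 participants, power is 80% for the score and 61% for a median split. With 280, it is 65% and 46%.

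**Check in a model of the planned kind.** A simulated log-linear mean model with robust variance was run with 400 participants, four 30-day windows, no dropout and attendance in days. Cuts ran from 50/50 to 20/80. The loss was 39% to 52% for a normal score and 42% to 57% for an assumed skewed one. The closed-form figures are therefore not optimistic for the cut.

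**The yes/no response.** In 10.4.1.1.2, N_i(t) is the cumulative number of positive results, and the screen is taken at four post-baseline assessments. Two readings of attendance follow:

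- One yes/no per assessment: the post-baseline count cannot exceed 4. In the window to week 4 (4 × 7 = 28 days), one attended day and 28 attended days both add 1.
- One yes/no per calendar day: the count is the number of days attended, up to 26 × 7 = 182 over 26 weeks, and nothing is lost.

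The protocol does not say which is meant. Modelling attendance on the drug screen makes the first reading the more natural one. No size is given for this part, because it depends on an attendance distribution that the protocol does not give.

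**The case against.** The best defence is that no median split or quartile cut is written anywhere. The only example given for the covariate is categorical, the model is described only as similar to the template, and 5.4.3.1.3 names the composite itself as the predictor. On this view the sentence was written for group contrasts and sits loosely over two graded predictors, with the coding left to a statistical analysis plan that is not at hand. This stands in part: a missing cut-point is not itself a fault of the protocol. But the indicator is a stated choice that applies to every listed hypothesis. An analysis plan that supplied a cut-point would carry that choice out, not correct it.

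For SOCRATES, 5.4.3.4.3 says the instrument is meant to show which stage a person is in, which gives grouping some basis. The hypothesis, however, is worded as higher versus lower readiness, and three subscales do not yield one two-way split.

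A reader might also infer that one meeting in a window certainly counts the same as daily attendance. The document does not establish that. In a recurrent-event model a yes/no per calendar day would already equal days attended, so this part is an ambiguity to be closed and not a demonstrated loss.

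Finally, 10.4.4 is headed exploratory, and 10.4 treats significant secondary findings as exploratory. That stands, and it limits the importance of the point.

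**Conclusion.** The point holds as a minor one. For two of the five exploratory subtype hypotheses, the protocol fixes a group indicator where a graded score is already collected and the planned model would accept it. For a roughly normal score with a linear effect, cut between the median and the top quarter, about 36% to 46% of the information on that predictor is lost. A hypothetical 80% power becomes 61% or 54%.

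A reader might be tempted to say that the subtype analyses as a whole throw away a third to a half of their information. The documents do not support that as an unconditional statement. The range covers only the predictor cut, only hypotheses 10.4.4.1.3 and 10.4.4.1.5, and only under assumptions about the score and the cut that the protocol neither gives nor excludes. Race/ethnicity, gender and drug type lose nothing by being indicators. Nor do the primary or key secondary conclusions depend on this coding. The yes/no attendance outcome needs a definition; its cost cannot be sized from the text.

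**What to change.** In the analysis paragraph of 10.4.4.1.5:

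- For 10.4.4.1.3, let Z_i be the continuous baseline ASI Psychiatric composite, per SD.
- For 10.4.4.1.5, let Z_i be one baseline SOCRATES subscale score, per SD, with the subscale named before the data are examined. If linearity is checked, report the check beside the result and do not use it to choose the coding.
- Keep group indicators for race/ethnicity, gender and drug type.
- Define the recurrent event as a calendar day with 12-step attendance on the Substance Use Calendar, so that N_i(t) is the number of days attended.

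The cost is wording in the protocol or the statistical analysis plan. The ASI-Lite, SOCRATES and the calendar are all in the Table 1 schedule, so no new data, visits or participants are needed.
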